## **6.3 Missing Data**

In general, missing values will remain as missing, i.e., no attempt will be made to impute missing values and only observed values will be used in data analyses and presentations.

#### Survival analysis

All patients not reaching any event at the end of follow-up or before their last assessment (for patients lost to follow-up) will be censored at the date of their last assessment visit. Patients receiving a liver transplant will be censored at the time of liver transplantation.

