## **Section 3: Study Methods**

## 3.1 Trial Design

This is an open label, multicenter, randomized, 2-arm parallel-group in a 1:1 ratio, trial to investigate the superiority of an "early tips" over glue obliteration in cirrhotic patients bleeding from gastric varices (non GOV1). The main end-point is death or clinically significant rebleeding during the 12-month follow-up, and randomized patients are followed until the end of the 12-month study period.

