## 5.2 Withdrawal/Follow-up

Criteria for stopping the study are:

- withdrawal of consent,
- liver transplantation,
- loss to follow up,
- enrollment of ineligible subjects.

Patients withdrawn from the study for withdrawal of consent, liver transplantation or loss to follow up will be censored at the date of withdrawal. Ineligible subjects will be excluded from the mITT analyses. Unless consent to analyze data is also withdrawn, all the data collected prior to withdrawal from the study will be considered for analysis.

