## **Section 6: Analysis**

#### 6.1 Outcome Definition

## Primary endpoint

Death (all cause) or clinically significant rebleeding (upper gastrointestinal bleeding whatever its origin, with event date) during the one-year follow-up.

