#### **Secondary endpoints**

Survival at Days 42, 90, 180 and 365

The survival rates will be compared with the same methods as described above for the analysis of composite event rate.

*Incidence of liver related death at Days* 42, 90, 180 and 365.

† ACLF: Acute on Chronic Liver Failure; **Grade 1:** a) Single kidney failure, b) Single liver, coagulation circulatory or respiratory failure + creatinine 1.5-1.9 mg/dL and/or HE I-II, c) Single cerebral failure (HE III-IV) + creatinine 1.5-1.9 mg/dL; **Grade 2:** 2 organ failures; **Grade 3:** 3 or more organ failure score.

The association of study arms with rebleeding hazard function will be tested using univariate and multivariate Cox models. The cumulative risk of rebleeding during follow-up in each arm will be estimated by calculating the cumulative incidence function (CIF) rebleeding at 12 months. In this approach, death for other causes during follow-up will be considered as a competing event.

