#### *Incidence of rebleeding during follow-up*

The association of study arms with rebleeding hazard function will be tested using univariate and multivariate Cox models. The cumulative risk of rebleeding during follow-up in each arm will be estimated by calculating the cumulative incidence function (CIF) rebleeding at 12 months. In this approach, death free of rebleeding during follow-up will be considered as a competing event.

Incidence of the other complications of liver cirrhosis during follow-up

The association of treatment group with the hazard function of other complications will be tested using univariate and multivariate Cox models. The cumulative risk of other complications during follow-up in each arm will be estimated by calculating the CIF at 12 months. In this approach, death free of complications during follow-up will be considered as a competing event.

Cumulative number of packed red blood cells required by each treatment arms.

Variation of MELD score between inclusion and 6 months in each arm

Number of days that patients spend in hospital during follow-up

Comparison between strategy groups will be performed with Student's t-test or the Mann-Whitney test, as appropriate.

Frequency of TIPS technical failure and TIPS complications: thrombosis, heart failure, infection and encephalopathy. Frequency of technical failure of GO and complications of GO: migration of glue, infection of the site of injection, significant bleeding during the procedure (hospital stay, blood transfusion, 3 g drop in hemoglobin).

This analysis will be performed on the safety population.

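### Liver transplantation is censored in every time-to-event analysis and is not a competing event in the cumulative incidence functions, and no sensitivity analysis covers it

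*SAP*

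**What the plan says.** Two places in the SAP set the rule, and they agree. Section 5.2 (Withdrawal/Follow-up) lists liver transplantation among the reasons for stopping the study and adds: "Patients withdrawn from the study for withdrawal of consent, liver transplantation or loss to follow up will be censored at the date of withdrawal". Section 6.3 (Missing Data, Survival analysis) repeats it without exempting any analysis: "Patients receiving a liver transplant will be censored at the time of liver transplantation".

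The rule therefore reaches these analyses in section 6.2:

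- **Primary endpoint**, defined in section 6.1 as "Death (all cause) or clinically significant rebleeding" during the one-year follow-up: Kaplan-Meier, log-rank and Cox.
- **Survival at Days 42, 90, 180 and 365:** the same methods as the primary endpoint.
- **CIF under the liver-related death heading:** "death for other causes during follow-up will be considered as a competing event". The method text there speaks of rebleeding, but the competing event named fits liver-related death, and it is read that way here.
- **CIF for rebleeding:** "death free of rebleeding during follow-up will be considered as a competing event".
- **CIF for other complications of cirrhosis:** "death free of complications during follow-up will be considered as a competing event".

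Transplantation is not a component of any endpoint, a competing event, a listed secondary outcome or the subject of a sensitivity analysis.

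**The concern.** There are two separate problems, and they concern different target quantities.

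**CIFs.** The plan uses CIFs so that an event which prevents the outcome is not handled as ordinary censoring, and it applies this to death. Transplantation takes away the diseased liver, so later ascites, hepatorenal syndrome, variceal bleeding or death from the native cirrhosis is prevented or becomes a different matter. Left as censoring, each transplanted patient is in effect replaced by patients still at risk, and the curve rises above the proportion who actually have the event.

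**Primary endpoint and survival.** Kaplan-Meier, log-rank and Cox assume that a patient censored at transplantation has the same later hazard as a comparable patient still followed. Section 5.1 excludes only Child-Pugh scores above 13 and hepatocellular carcinoma outside the Milan criteria, so transplantation within the year is foreseeable. If it follows deterioration, the assumption fails. If its frequency or indication differs by arm, which is possible in an open-label trial, the hazard ratio is affected. A death after transplantation but within the year is also lost from an endpoint that includes death from any cause.

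**Working it through.** **Anchor.** The SAP has no figure for transplantation. Its sample size (section 3.3: 40% v 15%, one-sided 5%, 80% power, 10% dropout) reproduces. With the hazard ratio taken as 0.15/0.40 = 0.375, Schoenfeld's formula gives 25.7 events; 25.7/0.55 = 46.7 per arm; 46.7/0.9 gives 52. It does not depend on this point.

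**Step 1: size of the CIF excess.** Assumptions: constant and independent hazards, and 12-month net transplant risks of 5%, 10% and 20%. The event risks of 40% and 15% echo the planned primary rates. The competing death risks of 15% and 10% are assumed. Each risk p becomes a hazard λ = −ln(1 − p). The 12-month CIF is

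λe/(λe + λo) × [1 − exp(−(λe + λo))],

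where λo is the death hazard alone if transplantation is censored, and the death plus transplant hazard if it competes.

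Example: event 40% (λe = 0.511), death 15% (0.163), transplantation 20% (0.223).
- Censored: 0.511/0.673 × (1 − e^−0.673) = 37.2%.
- Competing: 0.511/0.896 × (1 − e^−0.896) = 33.7%.

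| Event / death risk | Transplant risk | CIF, transplant censored | CIF, transplant competing | Excess (points) |
|---|---|---|---|---|
| 40% / 15% | 5% | 37.2% | 36.3% | 0.8 |
| 40% / 15% | 10% | 37.2% | 35.5% | 1.7 |
| 40% / 15% | 20% | 37.2% | 33.7% | 3.4 |
| 15% / 10% | 5% | 14.3% | 13.9% | 0.3 |
| 15% / 10% | 10% | 14.3% | 13.6% | 0.7 |
| 15% / 10% | 20% | 14.3% | 12.8% | 1.4 |

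Excesses are computed before rounding. In relative terms they run from about 2% to 11%.

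**Step 2: when sicker patients are transplanted more often.** In a simulation, 30% of patients had sixfold hazards of the event, of death and of transplantation, with the mean transplant hazard matching a 20% risk. The CIF was 39.3% with transplantation censored, 36.9% with it competing and 40.6% in a world without transplantation. Censoring then estimates neither quantity: it is too high for actual incidence and too low for the risk without transplantation.

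**Step 3: how far a transplant-inclusive primary endpoint could move.** Take the planned 40% (glue) and 15% (TIPS) with an independent transplant risk t in each arm. The risk of event or transplantation is 1 − (1 − p)(1 − t), and the hazard ratio is the ratio of log event-free proportions. Without transplantation it is ln 0.85/ln 0.60 = 0.32.

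| Transplant risk, glue / TIPS | Glue | TIPS | Hazard ratio |
|---|---|---|---|
| 10% / 10% | 46.0% | 23.5% | ln 0.765/ln 0.540 = 0.43 |
| 5% / 15% | 43.0% | 27.75% | ln 0.7225/ln 0.570 = 0.58 |
| 15% / 5% | 49.0% | 19.25% | ln 0.8075/ln 0.510 = 0.32 |

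These are values of a different endpoint. They do not estimate the bias of the planned analysis; they show that the result can be sensitive to transplantation and that the amount depends on its balance between arms.

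**The case against.** The strongest reply is that the rule is prespecified, that sections 5.2 and 6.3 agree, and that censoring at a competing event is accepted for cause-specific hazards. The last point stands: the Cox models for the secondary events need no change. It does not cover the CIFs, where the choice of competing events determines what is estimated.

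Transplantation does not preclude everything. Section 6.1 counts upper gastrointestinal bleeding of any origin as rebleeding, and complications include bacterial infection and jaundice. That also stands, which is why the claim is limited to most of these outcomes. A transplant for tumour may also have nothing to do with failure of the assigned treatment, and the SAP says nothing on indications by arm.

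Three stronger readings are tempting, and the document supports none of them.

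- **Transplanted patients count as event-free.** They do not. They leave the risk set and are assumed to carry the hazard of those who remain. The issue is informative censoring.
- **The rule favours one particular arm.** Adding transplants to the TIPS arm alone and calling them failures would suggest so, but that fixes the direction by assumption and changes the endpoint. Step 3 shows a shift in one scenario and almost none in its mirror image.
- **Section 3.1 contradicts section 5.2.** Section 3.1 says that "randomized patients are followed until the end of the 12-month study period". This is a general design statement, and section 5.2 lists its exceptions, including consent withdrawal and loss to follow-up. It does not show that follow-up after transplantation was intended.

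**Conclusion.** The point holds in limited form. As written, the CIFs overstate the incidence patients experience, by about 0.3 to 3.4 percentage points at assumed 12-month transplant risks of 5% to 20%. At the lower end this is small. The figures rest on constant, independent hazards and on event and death risks chosen for illustration.

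For the primary endpoint and survival, the conclusion is qualitative. Censoring may be informative, any bias in the hazard ratio could go either way, and its size cannot be derived from the SAP. Deaths after transplantation are left out of an all-cause death endpoint with no analysis to show whether this matters. The planned primary analysis remains usable, but its robustness to this rule is not examined.

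**What to change.** 1. In section 6.2, name liver transplantation as a competing event together with death in the CIFs for liver-related death, rebleeding and complications of cirrhosis. Leave the cause-specific Cox models as they are.
2. Keep the primary analysis. Add one prespecified sensitivity analysis, of the primary endpoint and of survival, in which transplantation counts as an event. Tabulate transplants by arm with date and indication.
3. Where vital status to Day 365 after transplantation is already available, report all-cause survival without censoring at transplantation as a further sensitivity analysis. The SAP does not say whether these data exist, so this step is conditional and asks for no change to follow-up.

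The cost is a few sentences in the SAP and modest programming. The downside is one or two extra results to report and slightly lower CIF estimates.

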#### 6.4 Harms

Safety analyses will be conducted in the safety population using the same evaluation period as for efficacy analyses (i.e. from randomization until end of 12-month follow-up).

The number of adverse events and SAE observed in each strategy group will be described and compared by using Chi-squared test or Fisher's exact test, as appropriate. Adverse events will be described in a table in order of decreasing frequency.

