## Glue obliteration procedure in control arm (Group B):

- Filling of varice(s) with tissue adhesive under endoscopic guidance will be initially performed in all patients under general anesthesia. The use of a Doppler EUS will be at the discretion of the practitioner.
- Endoscopic control (and further glue obliteration session if necessary) will be performed in the group B between day-5 and day-8 after the initial bleeding. A new session will then be proposed at days 42+/-7, 90+/-14, 180+/-14 and 365+/-14.
- Endoscopic reports will be systematically collected. The report should specify the topography and size of varices (if possible, a picture will be collected), the type of glue, the volume injected as well as the proportion of Lipiodol.
- In the case of coexistence of esophageal varices, the latter will be systematically treated during the same endoscopic session by band ligation.
- In patients randomized to group B the decision of "salvage TIPS" will be left to the discretion of the investigator and will be then considered as a failure of the endoscopic procedure.
- When placing TIPS for another indication during follow-up in the group B, the patient will be censured at the date of installation of the device.
- In the absence of contraindication, a non-selective beta-blocker treatment will be proposed in the group B according to the recommendations of the Baveno VI Consensus Workshop 2015 (14).

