## 3.3 Sample size

The sample size is calculated with a projected rate of composite event of failure at 12 months of 15% in the group "TIPS" [estimated from Garcia Pagan, New Engl J Med 2010] versus 40% in the group « glue» [estimated from Hou, Gastrointest Endosc 2009].

A number of 52 patients in each group will achieve 80% power to detect TIPS superiority using a one-sided logrank test at a 0,050 significance level, with a proportion dropping out of both groups of 10%.

Total number of scheduled patients recruited or observations collected: 104.

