## **Section 4: Statistical Principles**

#### 4.1 Confidence Intervals and P-values

All tests will be two-sided, with p values of less than 0.05 denoting statistical significance. 95% confidence interval will be used to report effect estimates of secondary endpoints.

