#### Safety population

By default, patients who underwent the procedure after randomization will be included in the safety population and assigned to the glue obliteration arm. Patients who underwent the early-TIPS procedure without regard for its successful completion will be included in the safety population and assigned to the early-TIPS arm. Patients who, for any reason, could not undergo either procedure will be excluded from the safety population.

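### SAP section 6.4 compares totals of adverse events by chi-squared or Fisher's test; taken as written, repeat events in one patient are treated as independent, so p-values are too small if events cluster within patients

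*SAP*

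**What the plan says.** Section 6.4 sets the rule for harms: "The number of adverse events and SAE observed in each strategy group will be described and compared by using Chi-squared test", with Fisher's exact test as the alternative. The window is 12 months, "from randomization until end of 12-month follow-up", and the analysis set is the safety population. Section 4.3 defines that population by the procedure a patient received: "Patients who, for any reason, could not undergo either procedure will be excluded from the safety population". This fixes who is included, not how often a patient may be counted.

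Section 4.1 applies the usual threshold: "All tests will be two-sided, with p values of less than 0.05 denoting statistical significance".

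No section says that each patient counts once in the harms comparison, gives a denominator for it, or names a method for recurrent adverse events.

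**The concern.** A chi-squared or Fisher test on a two-by-two table assumes that the units in its cells are independent. Patients meet that condition; several events in one patient generally do not. An event total also cannot be set over the number of patients as a proportion, because it can exceed that number.

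Repeat events are likely here. The complications that section 6.1 lists (infection, ascites, encephalopathy, hepatorenal syndrome) are related to one another and can recur. In the glue arm, repeated endoscopy adds opportunities: after the control at days 5 to 8, "A new session will then be proposed at days 42+/-7, 90+/-14, 180+/-14 and 365+/-14".

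At stake is the p-value attached to overall adverse events and SAEs for an invasive strategy in an open-label trial. A spurious difference could count against either arm. If the unit stays open, it could also be chosen after the data are seen.

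**Working it through.** The SAP states no figure for this comparison, so there is none to reproduce. The check asks what happens to a nominal 5% test on event totals when the arms do not differ.

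**Inputs from the SAP**
- Two-sided 5% level (section 4.1).
- Equal allocation, "2-arm parallel-group in a 1:1 ratio" (section 3.1).
- 52 patients per arm (section 3.3).
- 12-month window (section 6.4).

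**Assumed, not in the SAP**
- Mean of 0.5 to 4 events per patient.
- Variance-to-mean ratio φ of the per-patient count. In a gamma-Poisson model with shape k, φ = 1 + mean/k. With no variation between patients, φ = 1.

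**Formula.** Let A and B be the event totals in two arms of n patients with the same mean m. The chi-squared statistic against an equal split is (A − B)²/(A + B). The variance of A − B is 2·n·m·φ, and A + B is about 2·n·m. The statistic therefore behaves as φ times a chi-squared variable with one degree of freedom, and

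type I error = 2 × [1 − Φ(1.96/√φ)].

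| φ | 1.96/√φ | Type I error |
|---|---|---|
| 1 | 1.960 | 5.0% |
| 2 | 1.386 | 16.6% |
| 3 | 1.132 | 25.8% |
| 4 | 0.980 | 32.7% |

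**Simulation.** 52 patients per arm, identical event rates, 40,000 replicates; type I error of the test on event totals:

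| Mean events per patient | No variation between patients | k = 2 | k = 1 | k = 0.5 |
|---|---|---|---|---|
| 0.5 | 4.9% | 7.7% | 10.9% | 16.1% |
| 1 | 5.2% | 10.6% | 16.9% | 25.4% |
| 2 | 4.9% | 16.5% | 25.6% | 38.1% |
| 4 | 4.9% | 25.5% | 38.0% | 51.1% |

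Formula and simulation agree. For example, mean 2 with k = 2 gives φ = 1 + 2/2 = 2: 16.6% by formula, 16.5% simulated.

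**Another table built from events.** Comparing one event type's share of all events between arms gave a type I error of 18.4%, 19.9% and 27.3% in three assumed clustered scenarios.

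**Patient as the unit.** In the same simulations, a chi-squared test on patients with at least one event gave 5.0% to 6.3% in every scenario with variation between patients. With no such variation and a mean of 4 it gave 1.2%, because almost every patient then has an event and the test is conservative.

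**The case against.** The strongest reply is that the authors meant patients and wrote loosely. Section 5.3 assigns chi-squared or Fisher to categorical variables. Section 6.2 assigns Student's t or Mann-Whitney to per-patient quantities such as red-cell units and hospital days. Naming chi-squared or Fisher in 6.4 therefore suggests a yes/no outcome per patient, and patients would supply the denominator that events lack.

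The SAP's wording elsewhere does not settle it. Section 6.1 counts patients lost to follow-up but counts infections as events. Section 6.2 refers in its text to patients with the composite event, while the matching table column is labelled as events. The patient reading is plausible, but it is nowhere stated, and the sentence in 6.4 names events.

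It is also fair to object that the statistic used above is not written in the SAP and that the dispersion values are assumed. Both objections stand. The percentages show what could happen under a literal reading and do not predict this trial's error rate.

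Three stronger inferences are not supported:
- **That confidence intervals for harms will be too narrow.** Section 6.4 specifies none, and section 4.1 promises intervals for secondary endpoints, among which total adverse events are not listed.
- **That this is the trial's main safety comparison.** The SAP does not call it that. Section 6.2 analyses cirrhosis complications by Cox models and cumulative incidence with death as a competing event, and reports procedure complications separately.
- **That unequal follow-up is ignored throughout.** Only the comparison in 6.4 lacks any allowance for it; sections 6.2 and 6.3 deal with death and censoring for the time-to-event endpoints.

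**Conclusion.** The point holds in a conditional form. As written, section 6.4 tests event totals with methods that need independent units, and no other section corrects this. If events cluster within patients, p-values are too small: about 17%, 26% and 33% type I error at assumed variance-to-mean ratios of 2, 3 and 4. At a ratio of 1 there is no inflation. Some clustering is likely given the recurring complications and the repeated procedures, but the SAP gives nothing from which to estimate it.

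A reader might infer that false-positive safety findings are certain. They are not: that would need both the literal reading and real clustering. If patients with at least one event were meant, the tests are suitable and the defect is an unstated unit. The primary endpoint and the separate analyses of cirrhosis complications are unaffected.

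**What to change.** Change the tested quantity in section 6.4. For example:

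> The number and percentage of safety-population patients with at least one adverse event, and with at least one SAE, will be compared between strategy groups by chi-squared or Fisher's exact test. Total numbers of events will be reported descriptively.

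If event totals are to be tested, name a method that allows for repeat events and length of follow-up. Negative binomial regression with log follow-up time as offset is one option.

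The cost is a sentence or two in the SAP. It should need no new data, since each recorded event belongs to an identified patient. The downside is that the patient-level test does not use the information on repeat events, and says little if nearly every patient has at least one. It also does not adjust for length of follow-up. The descriptive event totals partly make up for the loss.
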